#### Follow-up of AEs and SAEs

- The investigator is obligated to perform or arrange for the conduct of supplemental measurements and/or evaluations as medically indicated to elucidate the nature and/or causality of the AE or SAE as fully as possible. This may include additional laboratory tests or investigations, histopathological examinations, or consultation with other health care professionals.
- After the initial AE/SAE report, the investigator is required to actively follow each subject at subsequent visits/contacts. If any information necessary to evaluate the suspected adverse reaction/event is missing or unknown, the investigator should seek such information from the source of the report when available and without delay forward it to Astex CS&RM, as soon as the information is available.
- It is the investigator's responsibility to follow all SAEs and any additional information pertaining to an SAE, such as, but not limited to clinically relevant information and SAE outcomes. This additional information should be reported to Astex CS&RM without delay as soon as the information is available.
- Additionally, the sponsor may request necessary information to evaluate serious adverse reaction/event and it is the investigator's responsibility to report this information without delay to Astex CS&RM, as soon as possible.
- If a subject dies during participation in the study or during a recognized follow-up period, the investigator will provide Astex CS&RM with a copy of any post-mortem findings including histopathology, if available.
- New or updated information will be recorded in the eCRF or otherwise communicated to Astex CS&RM within 24 hours of receipt of the information. If the new or updated information is entered into the EDC system, it will automatically be sent to Astex CS&RM.

### **Lost to Follow-up and Stopping of AE/SAE Collection**

- If the investigator has determined that the subject is lost to follow-up, no further collection of AE/SAE information is required. Investigator shall document in the appropriate CRF that the subject was lost to follow-up.
- All AE/SAE should be collected and reported to the sponsor (Astex CS&RM), 30 days following the last dose of the study treatment (investigational drug or control drug). However, if the investigator becomes aware of an SAE or of a death at any time beyond 30 days after the last dose, and he/she considers the event to be reasonably related to the study treatment or study participation, the investigator must promptly notify the sponsor and the information should be reported without delay and as soon as the information is available (Section 8.5.1).
- If the subject starts a new anticancer treatment within those 30 days, including a new investigational treatment, the stop date for reporting obligations for this study will be the date when the subject started the anticancer therapy, or the 30 days whichever occurs earlier.
- If the subject has withdrawn full informed consent to participate in the study, investigator should not collect AE/SAE data beyond the date of withdrawing informed consent.
- If the sponsor chooses to terminate or end the study, the sponsor will communicate expectations for data collection, including AE/SAEs.

#### **10.5.4 Reporting of Overdose or Other Medication Errors:**

**It is the responsibility of the investigator/site personnel to report to Astex CS&RM overdose or other medication errors**

**If an overdose or other medication error should occur, please proceed as follows:**

- If no AE/SAE occurred as a result of the medication error, document the medication error as a protocol deviation according to the Protocol Deviation guidance.
- If an AE occurred as a result of the medication error, document as an AE in the EDC system as well as a protocol deviation according to the Protocol Deviation guidance.
- If an SAE occurred as a result of the medication error, document as an SAE in the EDC system as well as a protocol deviation according to the Protocol Deviation guidance.

### 10.5.5 Reporting of SAEs

#### SAE Reporting to Astex CS&RM via an Electronic Data Capture Tool

- The primary mechanism for reporting an SAE to Astex CS&RM will be the electronic data capture (EDC) tool.
- Study center staff will enter the SAE data into the EDC system as soon as it becomes available, but no longer than 24 hours from receipt of the information. The EDC system will automatically send a report to Astex CS&RM.
- If a causality assessment is not provided, the default assessment will be ‘related’, for safety reporting purposes.
- After the study is completed at a given site, the EDC tool will be taken off-line to prevent the entry of new data or changes to existing data.
- If an investigational site receives a report of a new SAE from a study subject or receives updated data on a previously reported SAE after the EDC tool has been taken off-line, then the investigational site staff can report this information on a paper SAE report form (see the following section).

#### SAE Reporting to Astex CS&RM when EDC Tool is Unavailable

- If the EDC tool is unavailable, the site will enter the SAE data via paper SAE report form within 24 hours of first becoming aware of the SAE and email to Astex CS&RM.
- Contact for SAE reporting is as follows: **[contact]**

## 10.6 Appendix 6: Disease Response Assessment Based on International Working Group Criteria

Response will be assessed in patient with MDS in part by using the 2006 IWG criteria ([Cheson et al 2006](#)), as defined in [Table 21](#). Criteria for hematologic improvement are defined in [Table 22](#).

**Table 21: Response Criteria in Myelodysplastic Syndromes (IWG 2006 Criteria)**

Category	Response Criteria (responses must last $\geq 4$ weeks)
CR	
 
• BM <math>\leq 5\%</math> myeloblasts with normal maturation of all cell linesa
 
• Persistent dysplasia will be noteda,b
 
• Peripheral bloodc
 
• Hgb <math>\geq 11</math> g/dL
 
• Platelets <math>\geq 100 \times 10^9/L</math>
 
• Neutrophils <math>\geq 1.0 \times 10^9/L^b</math>
 
• Blasts 0%
 

PR	All CR criteria if abnormal before treatment except: 
 
• BM blasts decreased by <math>\geq 50\%</math> over pretreatment but still <math>>5\%</math>
 
• Cellularity and morphology not relevant
 

Marrow CR	BM $\leq 5\%$ myeloblasts and decrease by $\geq 50\%$ over pretreatment b Peripheral blood: if HI responses, they will be noted in addition to marrow CR b
Stable Disease	Failure to achieve at least PR, but no evidence of progression for $>8$ weeks
Failure	Death during treatment or disease progression characterized by worsening cytopenias, increase in percentage of BM blasts, or progression to a more advanced MDS FAB subtype than pretreatment
Relapse after CR or PR	At least 1 of the following: 
 
• Return to pretreatment BM blast percentage
 
• Decrement of <math>\geq 50\%</math> from maximum remission/response levels in granulocytes or platelets
 
• Reduction in Hgb concentration by <math>\geq 1.5</math> g/dL or transfusion dependenced
 

Cytogenetic Response	Complete: Disappearance of chromosomal abnormality without appearance of new ones Partial: At least 50% reduction of the chromosomal abnormality
Disease Progression	For patients with: 
 
• Less than 5% blasts: <math>\geq 50</math> increase in blasts to <math>>5\%</math> blasts
 
• 5%-10% blasts: <math>\geq 50\%</math> increase in blasts to <math>>10\%</math> blasts
 
• 10%-20% blasts: <math>\geq 50\%</math> increase in blasts to <math>>20\%</math> blasts
 
• 20%-30% blasts: <math>\geq 50\%</math> increase in blasts to <math>>30\%</math> blasts
 
 Any of the following: 
 
• At least 50% decrement from maximum remission/response in granulocytes or platelets
 
• Reduction in Hgb by <math>\geq 2</math> g/dLd
 
• Transfusion dependenced
 

BM=bone marrow; CR=complete response; FAB=French-American-British classification; Hgb=hemoglobin; HI=hematologic improvement; IWG=International Working Group; MDS=myelodysplastic syndromes; PR=partial remission.

a Dysplastic changes should consider the normal range of dysplastic changes.

b Modification to IWG response criteria

c In some circumstances, protocol therapy may require the initiation of further treatment (eg, consolidation, maintenance) before the 4-week period. Such patients can be included in the response category into which they fit at the time the therapy is started. Transient cytopenias during repeated chemotherapy courses should not be considered as interrupting durability of response, as long as they recover to the improved counts of the previous course.

d Impact of anemia must be deemed disease-related and not due to study treatment.

Source: [Cheson et al 2006](#)

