#### Type of Participant and Disease Characteristics

- 2) Histological confirmation of previously untreated MDS (ie, no HMA, chemotherapy, or allogenic SCT) per World Health Organization 2016 classification with  $<20\%$  BM blasts per marrow biopsy/aspirate at screening.
- 3) Projected life expectancy of at least 3 months.
- 4) Overall IPSS-R score  $\geq 3.5$  MDS (intermediate risk or higher).
- 5) Eastern Cooperative Oncology Group (ECOG) performance status (PS) of  $\leq 2$ .
- 6) Hematopoietic stem cell transplant (HSCT) eligible without any pre-arranged HSCT on Cycle 1 Day 1, or HSCT ineligible.
- 7) Hemoglobin  $\geq 9$  g/dL on the first day of drug administration, transfusions allowed.
- 8) Blood type and screen (ABO/Rh) along with extended red blood cell phenotyping or genotyping completed prior to study drug treatment.
- 9) Willing to undergo blood transfusions as per parameters of protocol and clinically necessary.
- 10) White blood cell count  $\leq 20 \times 10^3/\mu\text{L}$  prior to first dose and throughout study. Hydroxyurea can be used to achieve this goal prior to and during the first 56 days of magrolimab administration.

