#### **8.3.1 Disease Response Assessment**

Disease assessment will follow IWG 2006 criteria ([Section 10.6](#)) and will include CR, HI, and ORR (including CR, mCR, or any HI). Other assessments will include duration of PFS, LFS, undetectable disease assessed by MRD, DOR, and OS. Disease response assessment will be determined based on BM evaluations and a corresponding PB sample along with transfusion requirements. Bone marrow evaluations must include aspirate (when feasible), biopsy, and cytogenetics. If hematologic recovery is in progress, a repeat CBC may be done no more than 7 days after the BM evaluation for response assessment. The BM biopsy and aspirate procedure will be conducted according to local standard practice at time points shown in the SoA ([Table 1](#)).

BM and PB samples adequate for analysis must be obtained in order to confirm response. BM biopsy and aspirate and a CBC must be repeated if the BM and/or PB sample are not interpretable by the investigator. A local laboratory will be used to assess BM and PB samples. BM samples should be Wright Giemsa or May Grunwald Giemsa stained. Detailed instructions for processing BM samples will be provided in the Laboratory Manual.

BM evaluations should be performed at screening and on Day 1 of every cycle (or within a 3-day window prior to Day 1) until an mCR is achieved (BM myeloblasts  $\leq 5\%$  and decrease by  $\geq 50\%$  over pretreatment). If an mCR is achieved, without meeting CR criteria, a follow-up BM evaluation should occur on Day 1 of the next cycle (or within a 3-day window prior to Day 1) to assess or confirm the possibility of CR. Thereafter, BM evaluation may occur as clinically indicated to monitor DOR as appropriately guided by PB counts after achieving a confirmed CR

but should occur at least every 3 cycles for the first year, then as clinically indicated. Results do not have to be fully available to start study treatment for that cycle.

Response will be assessed by the investigator and derived programmatically based on the 2006 IWG criteria ([Cheson et al 2006](#)). Further details of the IWG criteria can be found in Section [10.6](#).

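### Marrow CR has no minimum baseline blast percentage and blast relapse has no floor, so subjects who enter with few blasts can be scored as responding or relapsing on counting noise

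*Combined protocol and SAP*

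**What the plan says.** Table 21 (Appendix 6) gives the marrow CR criterion as "BM $\leq 5\%$ myeloblasts and decrease by $\geq 50\%$ over pretreatment". Section 8.3.1 repeats it when it sets the marrow schedule. Neither place names a minimum pretreatment blast percentage. Section 8.3.1 counts marrow CR as response: "ORR (including CR, mCR, or any HI".

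The row headed "Relapse after CR or PR" has three limbs, any one of which suffices. The blast limb reads "Return to pretreatment BM blast percentage" and sets no absolute level. The progression row of the same table does set one: a subject in the class "Less than 5% blasts" must rise above 5%.

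Two other provisions bear on the point. The header of Table 21 says "responses must last $\geq 4$ weeks". Sections 6.3 and 8.3.1 have response both assessed by the investigator and derived by a program from these criteria.

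On entry, Section 5.1 caps marrow blasts below 20% and requires an IPSS-R score of at least 3.5, "MDS (intermediate risk or higher". It sets no lower blast limit.

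**The concern.** A criterion built on a relative fall needs something to fall from. In a subject who starts at 2%, the first half of the mCR rule (at most 5%) already holds before treatment, so mCR rests wholly on the halving. On a marrow differential that is a difference of a few cells. At a baseline of 0% a fall of half is undefined.

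The relapse limb has the opposite fault. The CR row needs at most 5% blasts and no fall at all. A subject who enters at 2%, recovers blood counts and shows normal maturation at 2% is in CR, yet blasts are already at the pretreatment value.

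At stake are ORR, which false mCRs can raise, and duration of CR and DOR, which false relapses can shorten. Sections 4.1 and 4.5 also list relapse after PR or CR among the grounds for ending study treatment, so the ambiguity reaches beyond the analysis.

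**Working it through.** **1. Can low-blast subjects enter?** Table 18 gives blasts of 2% or less 0 points. Poor cytogenetics (3) plus Hgb 8 to <10 (1) scores 4.0, which meets the 3.5 cut. The non-blast items give 5 cytogenetic × 3 Hgb × 3 platelet × 2 ANC = 90 combinations. Of these, 51 reach 3.5 with blasts ≤2%, and 69 do so with blasts >2% to <5% (1 point). These are combinations, not patients, and show only that the route is wide.

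**2. Size of the mCR noise.** The plan states no figure to reproduce. Assumptions: n = 200 or 500 cells per marrow (not given in the documents), constant true blast fraction p, and independent binomial counts. Let B be the baseline count, restricted to B/n ≤ 5%. A follow-up count F qualifies if F ≤ B/2, so q(B) = P(F ≤ B/2).

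Example: n = 200, p = 2%, B = 4. Then q = P(F ≤ 2) = 0.0176 + 0.0718 + 0.1458 = 0.235.

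- One marrow: q, averaged over B.
- Any of three marrows: 1 − (1 − q)³, averaged over B.
- Two consecutive of three, as a stand-in for the 4-week rule: q² + q² − q³ = 2q² − q³, averaged over B. In the example, 2(0.0553) − 0.0130 = 0.098.

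| Cells | True blasts | One marrow | Any of three | Two consecutive of three |
|---|---|---|---|---|
| 200 | 2% | 21.7% | 46% | 11.5% |
| 200 | 3% | 13.6% | 33% | 5.2% |
| 200 | 4% | 6.9% | 19% | 1.4% |
| 500 | 2% | 8.2% | 21% | 2.6% |
| 500 | 3% | 3.8% | 10% | 0.7% |
| 500 | 4% | 1.0% | 3% | 0.05% |

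**3. Effect on ORR.** The share of subjects entering with blasts ≤5% is not in the documents; assume 20-40%. With the persistence rule, the effect runs from 0.20 × 0.05% = 0.01 points to 0.40 × 11.5% = 4.6 points, before allowing for subjects who respond anyway.

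**4. Relapse against progression.** Consider a CR subject with 2% at baseline.

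| Marrow after CR | CR blast limit (≤5%) | Relapse, blast limb | Progression, blast limb |
|---|---|---|---|
| 1% | met | not met | not met |
| 2% | met | met | not met |
| 3% | met | met if read as at or above baseline | not met |
| 6% | not met | met | met |

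The second line is the contradiction: one marrow satisfies CR and relapse together. If true blasts never change from 2-4%, P(F ≥ B) at a single marrow is 53-57% for either cell count, so the limb carries almost no information in such a subject. This is not an estimate of the false-relapse rate, because it does not condition on reaching CR.

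The row cannot be reached through PR at low blasts. PR needs a fall of at least half to a value still above 5%, hence a baseline above 10%. Subjects with mCR alone are outside the row.

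**The case against.** The strongest reply is that the plan already has safeguards. The 4-week header and the next-cycle marrow in Section 8.3.1 filter out single chance results, the investigator assesses response alongside the program, and the SAP is still to be finalised before any efficacy assessment. Secondary endpoints are descriptive, and sample size and futility rest on CR alone. All of this stands. It is why the wording here is that subjects can be misclassified, not that they will be. None of it adds a baseline condition or a floor, and a program will apply the rows as written.

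Overlap shrinks the effect further. In ASTX727-02, ORR without responders by mCR alone was 61.7 − (32.3 − 16.5) = 45.9%. If that share of low-blast subjects responded anyway (assumption), the upper end becomes 4.6 × (1 − 0.459) = 2.5 points.

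A reader might infer four stronger things that the documents do not support.

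- An ORR inflation of up to about 19 points follows from the any-of-three column (0.40 × 46%), but that ignores the 4-week rule in the same table.
- Bias in the primary CR rate does not follow, since mCR is not part of it.
- It might seem that a false mCR ends the marrows that would find CR. Section 8.3.1 requires another marrow at the next cycle and then at least every 3 cycles in the first year, and the marrow footnote to Table 1 fixes marrows at Cycles 3, 5 and 7 and every 3 cycles after, whatever the response.
- A numerical loss of DOR cannot be computed, because the problem is confined to low-blast subjects who reach full CR and their number is unknown.

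**Conclusion.** The point holds. As written, eligible subjects with few blasts can be scored mCR, and so counted in ORR, on counting noise. Likely size: about 1-22% per single marrow, about 0.05-12% with two consecutive qualifying marrows of three, and about 0-5 ORR points before overlap. These figures rest on the assumed cell counts, constant true blasts of 2-4%, the reading of the 4-week rule as a second marrow, and the assumed 20-40% low-blast share. Binomial error leaves out sampling and reader variation, so the per-marrow figures are more likely low than high on that account.

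The relapse and progression rows conflict for low-blast subjects in CR. That follows from the text and needs no assumption. Its effect on duration of CR and DOR is in the direction of shortening, with no size attached. No sample-size, power or futility figure depends on either part.

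**What to change.** **Marrow CR.** In the mCR row of Table 21, in the ORR definition and in Section 8.3.1, restrict mCR to subjects with pretreatment marrow blasts above 5%. Footnote b already marks this row as modified from the IWG criteria, so a further stated condition fits the table. At a true 2% and 200 cells, averaging over all baseline counts, noise mCR at one marrow drops from 21.8% to 0.2%. The gain is smaller near the threshold: at a true 4% it drops from 10.9% to 5.2%, because some baselines are read above 5% by chance. The cost is one line in the table, its echo in two places and in the response program, and a slightly lower reported ORR.

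**Relapse.** Reconcile the blast limb of the relapse row with the progression row for subjects whose pretreatment blasts are low, and state which governs when a marrow still meets CR. Do this before the response program is finalised. Because relapse is also a ground for stopping treatment, the choice of rule belongs to the sponsor and investigators, and none is proposed here. The haemoglobin, platelet and granulocyte limbs are not in question.

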**Table 22: Criteria for Hematologic Improvement**

Hematologic Improvement	Response Criteria (responses must last <math>\geq 8</math> weeks)
Erythroid response (pretreatment, $<11$ g/dL)	1) Hgb increase by $\geq 1.5$ g/dL and/or 2) Relevant reduction of units of RBC transfusions by an absolute number of at least 4 RBC transfusions/8 weeks compared with the pretreatment transfusion number in the previous 8 weeks. Only RBC transfusions given for a Hgb of $\leq 9.0$ g/dL pretreatment will count in the RBC transfusion response evaluation.
Platelet response (pretreatment, $<100 \times 10^9$ /L)	1) Absolute increase of $\geq 30 \times 10^9$ /L for subjects starting with $>20 \times 10^9$ /L platelets and/or 2) Increase from $<20 \times 10^9$ /L to $>20 \times 10^9$ /L and by at least 100%.
Neutrophil response (pretreatment, $<1.0 \times 10^9$ /L)	At least 100% increase and an absolute increase $>0.5 \times 10^9$ /L.

Hgb=hemoglobin; RBC=red blood cell

Source: Criteria from 2006 MDS criteria (adapted from [Cheson et al 2006](#))

## 10.7 Appendix 7: Modifications During a COVID-19 Health Emergency

### 10.7.1 General Information

This section describes modifications to the study protocol which may be implemented to allow flexibility in conducting this study during the current COVID-19 public health emergency or re-emergence of the same, while maintaining safety of trial participants, maintaining compliance with GCP, and minimizing risks to trial integrity. These modifications are intended to remain in effect only for the duration of the public health emergency related to COVID-19 and only in instances where the study cannot be conducted per the protocol.

Any modifications to the study protocol must be discussed with the Astex medical monitor before implementing.

### 10.7.2 Study Status

In extenuating circumstances (eg, during the COVID-19 pandemic), Astex may implement all or some of the following modifications:

- Temporarily pause recruitment of new trial subjects.
- Extend the duration of the study.
- Postpone activation of study centers that have not been initiated.
- Transfer study subjects to investigational study centers away from high-risk zones or closer to their home.
- Convert physical visits to phone or video visits.
- Modify to ensure that only strictly necessary visits are performed at study centers.
- Allow laboratory tests and/or diagnostic tests to be conducted at a local laboratory/facility authorized/certified to perform such tests.
- Make changes to the per-protocol informed consent process in accordance with IRB/IEC and institutional guidelines.

### 10.7.3 COVID-19 Benefit/Risk Assessment

The safety of each trial participant is of primary importance. Astex will continually reassess the risks of conducting this clinical trial against the anticipated benefit for trial participants as the COVID-19 situation evolves and implement and document changes accordingly.

It is possible that local circumstances may lead to a local change in risk assessment (eg, an escalation of the pandemic within a certain region); therefore, the need to implement additional measures may arise. Investigators may be asked to complete a risk assessment questionnaire provided by Astex. This assessment should be documented in the investigator's site master file and communicated to Astex.

## 10.7.4 Modifications to Study Conduct

### 10.7.4.1 Alternative Methods for IMP Shipment

In extenuating circumstances (eg, during the COVID-19 pandemic) where standard approaches to dispensing study drug to subjects are not possible, alternative methods for dispensing study drug to subjects may be used. Astex will work with individual sites to find acceptable alternative arrangements (eg, shipment of study drug from study center pharmacies to subjects) that assure compliant control of study drug and acceptable safety monitoring. Alternative methods for drug dispensing must be reviewed by Astex before implementing.

